10.0 Statistical Analysis Plan

The primary objective of the analysis will be to compare the effect of intraoperative oxygenation on oxidative damage and organ injury. The primary endpoint of Aim 1 will be change in serum creatinine from baseline (defined as the most recent creatinine measured prior to surgery) to postoperative day 2. The primary endpoint of Aim 2 will be F₂-isoprostanes/isofurans measured in plasma.

Sample Size Calculations

We calculated the subject sample size based on data from the Vanderbilt Statin AKI Cardiac Surgery RCT (PI: [name]).²⁷ Data from this study indicate that mean serum creatinine concentrations increase 0.08 ± 0.37 mg/dl from baseline to postoperative day 2. We have powered the present randomized clinical trial conservatively, particularly since consensus criteria for AKI diagnosis define AKI as a 0.3 mg/dl rise in serum creatinine from baseline to postoperative day 2.²⁹ With 200 subjects, we will have 80% power to detect a 0.15 ± 0.375 mg/dl difference in serum creatinine between groups, with a type I error rate of 5%. In addition, with 200 subjects we will have 80% power to detect a 20 ± 50 pg/ml difference in plasma F₂-isoprostanes between groups, and we observed that physiologic oxygenation was associated with 35 ± 30 pg/ml less increase in plasma concentrations of F₂-isoprostanes among pilot subjects compared to hyper-oxygenated subjects. To account for a potential dropout rate of 10%, we plan to recruit 222 subjects.

For the endothelial function sub-study, we calculated the sample size based on a prior study of patients administered an oral antioxidant, treatment improved FMD 2.3% more than placebo with a standard deviation of 2.0%.³⁰ With 80 patients, we will have greater than 80% power to detect a 2%

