difference in FMD change from baseline to ICU admission between subjects randomized to hyper-oxygenation vs. physiologic oxygenation with a standard deviation of 3.0%, with a type I error rate of 0.05 (primary analysis sub-study Aim 1). We will have 94% power to detect a correlation of 0.2 or greater between intraoperative F₂-isoprostan concentrations and postoperative FMD (primary analysis sub-study Aim 2) with standard deviation of 20 pg/ml F₂I and 10 for regression errors. We will have greater than 80% power to detect a 2% difference in FMD between patients who do and do not develop postoperative delirium in the ICU, assuming a delirium incidence of 23.4% among all ROCS trial subjects, similar to that in the Statin AKI Cardiac Surgery RCT. Sub-study Aims 1 and 2 will be completed with 80 ROCS trial subjects and sub-study Aim 3 with all 200 patients.

Randomization

The study's statistician will be responsible for centralized randomization and subject assignment based on stratification in a permuted block fashion, using a sequence of blocks with sizes either two or four, where the sizes are selected uniformly at random. Randomization will be stratified by chronic kidney disease (defined as stage 3, 4, or 5 CKD [i.e., an eGFR <60 ml/min/1.73m²]) and use of cardiopulmonary bypass during surgery. Thus, there will be four randomization strata. We use the modification of diet in renal disease formula to estimate GFR for randomization stratification. This scheme provides ample subject assignment to all strata.

Data Analysis Plan

Standard graphing and screening techniques will be used to evaluate data quality. Data include patient demographics, baseline and intraoperative clinical characteristics, treatment toxicity and clinical outcomes. Summary statistics of study arms for both numerical and categorical variables will be provided to describe the study sample. Continuous variables will be summarized with the 50th (10th, 25th, 75th, 90th) percentiles, mean and standard deviation, and categorical variables will be summarized with the counts and percentages. For outcomes measured at a single time point, comparisons across randomization groups will be implemented using the Fisher's exact test or Pearson chi-square test for categorical variables, and the Wilcoxon rank sum test or Student T-test for quantitative outcomes, as appropriate. The Clopper-Pearson and Wald methods will be used to construct 95% confidence intervals for the between group effects.

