ischemic attack, and stroke between treatment groups. Similar to the primary analysis, we will implement logistic, proportional odds and linear regression analyses for binary, ordinal or highly skewed, and continuous outcomes, respectively, using a propensity score adjusted approach, if warranted. Potential impactful covariates included in these models will be specific to each outcome (for example, history of chronic obstructive pulmonary dysfunction would be appropriate covariate for time to extubation analysis).

To test the hypothesis (Endothelial function sub-study) that intraoperative physiologic oxygenation improves postoperative endothelial function (sub-study Aim 1) we will compare change from baseline in FMD (primary endpoint of Endothelial function sub-study), reactive hyperemia index, PAI-1, and E-selectin and the amplitude of endothelium-dependent vasodilation randomized subject groups in the first 80 subjects to complete the ROCS trial. The change from baseline in FMD, RHI, PAI-1, and E-selectin and the amplitude of endothelium-dependent vasodilation will be compared between oxygenation groups using Student's t-test or Mann Whitney U test. To test the hypothesis that endothelial dysfunction correlates with increased oxidative stress during cardiac surgery (sub-study Aim 2) we will compare perioperative concentrations of F₂-isoprostanes and isofurans to endothelial function assessments and plasma markers of endothelial activation at ICU admission in the first 80 subjects to complete the ROCS trial using linear regression and adjust for baseline measurements of endothelial function, and confounders such as randomized treatment group, blood transfusion, and duration of CPB. To test the hypothesis that perioperative endothelial dysfunction is associated with organ injury (sub-study Aim 3) we will compare baseline, postoperative, and change from baseline FMD, reactive hyperemia index, PAI-1, and E-selectin and the amplitude of endothelium-dependent vasodilation to markers of AKI, delirium, myocardial injury, and additional secondary endpoints using logistic, linear, or proportional odds regression as appropriate in the total cohort (N=200). We will review, interpret, and report results from sub-study Aims 1 and 2 based on statistical report from [name] but will remain blinded to treatment assignments in these 80 subjects until the entire 200 patient cohort is completed.

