Every effort will be made to avoid missing data. Any methods of missing data imputation (e.g. multiple imputation using the chained-equations method) will be used cautiously as sensitivity analyses; and the analysis of results with imputation would be interpreted in the context of corroboration with the analyses without imputation. The primary analysis will be intention-to-treat. Before data unblinding, [name] will examine any protocol deviations and identify a list of protocol violators. In addition to the intention-to-treat analysis, a secondary per-protocol analysis will be conducted.

Specific inferences on the effects of interest will be made by reporting point estimates, along with 95% confidence intervals. Hypotheses will be tested at a two-sided significance level of $\alpha=0.05$. This data analysis plan will be carried out using the statistical analysis package R (R Development Core Team).

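### Endothelial sub-study Aim 2: the stated 94% power belongs to a regression slope of 0.2 (correlation about 0.37); for a correlation of 0.2 in 80 subjects it is about 43%

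*Combined protocol and SAP*

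**What the plan says.** Section 10.0, Sample Size Calculations, gives one power statement for the primary analysis of sub-study Aim 2: "We will have 94% power to detect a correlation of 0.2 or greater between intraoperative" F2-isoprostane concentrations and postoperative FMD. The sentence adds an SD of 20 pg/ml for F2-isoprostanes "and 10 for regression errors", the latter without a unit. The same paragraph assigns 80 subjects to sub-study Aims 1 and 2.

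The Data Analysis Plan in the same section runs the Aim 2 analysis "in the first 80 subjects to complete the ROCS trial using linear regression" and will "adjust for baseline measurements of endothelial function, and confounders such as randomized treatment group, blood transfusion, and duration of CPB". The general testing rule is two-sided at 0.05.

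Two other SDs in the sample size text bear on the inputs. FMD change for sub-study Aim 1 is compared "between subjects randomized to hyper-oxygenation vs. physiologic oxygenation with a standard deviation of 3.0"%. For the main trial, "we will have 80% power to detect a 20 ± 50 pg/ml difference in plasma" F2-isoprostanes.

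**The concern.** The power of a test of a correlation depends on the correlation, the sample size and alpha. It does not depend on the SD of either variable. A correlation of 0.2 is weak, and 80 subjects are too few to detect it reliably, so 94% is implausible on its face. That the sentence supplies a predictor SD and an error SD suggests a slope calculation whose result was then labelled a correlation.

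The label matters because it changes how a null result would be read. The Aim 2 hypothesis is itself worded in terms of correlation, so a reader will take 0.2 as r. With 94% power believed, a non-significant result in the first 80 subjects would look like strong evidence against any correlation of 0.2 or more. It would not be: if the observed correlation were 0, the 95% interval would be about -0.22 to 0.22, which still contains 0.2. Results for sub-study Aims 1 and 2 are to be reviewed and reported on these 80 subjects.

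**Working it through.** **Inputs.** From Section 10.0: n = 80; effect 0.2; SD of F2-isoprostanes 20; SD of regression errors 10; stated power 94%. Two-sided alpha 0.05 comes from the general testing rule. The Aim 2 sentence gives no alpha of its own, but sub-study Aim 1 also uses 0.05.

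**1. Reproducing the 94%: 0.2 as a slope.** For the t-test of a simple regression slope, the noncentrality is slope × SDx × √n / SDerror = 0.2 × 20 × √80 / 10 = 3.58, on 78 degrees of freedom. Power is 94.2% (noncentral t); simulation with a random predictor gives 93%. The stated figure is reproduced.

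**2. The correlation this slope implies.** The explained SD is 0.2 × 20 = 4, so r = 4 / √(4² + 10²) = 4 / √116 = 0.37.

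**3. 0.2 as a correlation, as the text says.**
- Fisher z: atanh(0.2) × √(80 − 3) − 1.96 = 0.2027 × 8.775 − 1.96 = −0.181, and Φ(−0.181) = 42.8%.
- Noncentral t: noncentrality 0.2 / √0.96 × √80 = 1.83, df 78, power 43.8%.
- Simulation: 43%.

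With the stated SDs, r = 0.2 is a slope of 0.2 / √0.96 × 10 / 20 = 0.102.

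**4. Other readings of 0.2 as a correlation.**

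| Reading | Power |
|---|---|
| n = 80, one-sided | 55-57% |
| n = 200, two-sided | 81-82% |
| n = 200, one-sided | 89% |
| n = 222, two-sided | 85-86% |
| n = 222, one-sided | 91-92% |

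None reaches 94%, and the plan limits Aim 2 to 80 subjects in any case.

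**5. What 80 subjects can detect, and what r = 0.2 would need** (Fisher z first, noncentral t second where two figures are shown).
- Smallest correlation with 80% power: tanh((1.960 + 0.842) / √77) = 0.309; 0.302.
- Smallest slope with 80% power, at the stated SDs: 0.159.
- Subjects needed for r = 0.2: 194 or 191 for 80% power; 304 or 299 for 94%.
- 95% interval half-width at an observed r of 0: tanh(1.96 / √77) = 0.220.

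**6. Covariate adjustment.** The plan adjusts for four named items but gives no variance figures, so these ranges are assumptions (four covariate degrees of freedom).
- Covariates unrelated to F2-isoprostanes that explain 25% of FMD variance turn a marginal r of 0.2 into a partial correlation of 0.2 / √0.75 = 0.231, with power 52-55%. At 50% explained, the partial correlation is 0.2 / √0.50 = 0.283, with power 70-74%.
- Covariates that share 10%, 25% or 50% of F2-isoprostane variance, with the effect size held fixed, lower power to 40%, 35% or 25%.

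**7. The two SDs.** Slope 0.2 with SDs of 20 and 10 implies a total FMD SD of √116 = 10.8, against 3.0% for FMD change in the preceding sentence. With a residual SD of 3.0 instead of 10, slope 0.2 would imply r = 4 / √(16 + 9) = 0.80. The F2-isoprostane SD is 20 here and 50 pg/ml in the main-trial calculation.

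**The case against.** The strongest reply is that the calculation is sound and only a word is wrong. The sentence quotes a predictor SD and an error SD, the planned analysis is a linear regression, and on those inputs the slope test has the power claimed. The plan also uses the language of correlation loosely for a regression association. This stands as the likeliest account of where 94% came from. It does not rescue the sentence, because a slope of 0.2 and a correlation of 0.2 are different effects here: the first is a correlation of 0.37.

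A second reply is that 43% is for an unadjusted test, while the plan adjusts for baseline endothelial function and other factors. In principle this is right. With covariates unrelated to F2-isoprostanes, power for a marginal r of 0.2 reaches about 92-94% at 72% of FMD variance explained and 94-96% at 74%. Nothing in the documents supports a figure that high. With r² = 0.04 and 72-74% explained by covariates, 22-24% of the variance is left, so a residual SD of 10 would mean a total FMD SD of about 10 / √0.24 = 20 to 10 / √0.22 = 21, beside the 3.0% stated for FMD change. The stated inputs also give 94% without any covariates.

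A third reply concerns the SD comparisons. FMD change is not postoperative FMD, and the SD of 50 pg/ml belongs to a between-group comparison in the main trial. That is fair: these are queries, not contradictions.

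Finally, the reach is limited. This is one aim of a sub-study, and the plan promises that "Specific inferences on the effects of interest will be made by reporting point estimates, along with 95% confidence intervals", so readers will see the precision actually achieved. That reduces the harm, but the power claim is still wrong as written.

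**Conclusion.** The concern holds. For the effect as labelled, unadjusted power with 80 subjects at two-sided 0.05 is 43-44%, about 50 percentage points below the stated 94%. The stated figure is reproduced only by reading 0.2 as a slope, which is a correlation of about 0.37. Unless covariates unrelated to F2-isoprostanes explain more than 70% of FMD variance, which the plan nowhere assumes, the phrase "detect a correlation of 0.2 or greater" and the figure 94% cannot both stand.

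The 43% needs no SD. It rests on n = 80 and on applying the plan's general alpha to Aim 2. The slope explanation is an inference that fits the quoted inputs and the planned regression. The figures for the adjusted model rest on assumed variance shares. The point should be fixed, but it is confined to sub-study Aim 2: the main trial's sample size and primary endpoints are not touched.

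**What to change.** The sponsor should state whether 0.2 is a slope or a correlation and make the power match. Wording that is true on the stated inputs under either intention:

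> With 80 subjects, an F2-isoprostane SD of 20 pg/ml and a residual SD of 10 [unit to be given], an unadjusted linear regression has 94% power at two-sided alpha 0.05 to detect a slope of 0.2 FMD units per pg/ml in absolute value (correlation about 0.37). Power for a correlation of 0.2 is about 43%. The smallest correlation detectable with 80% power is about 0.31.

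Separately, check the residual SD of 10 against the 3.0% used for FMD change, and the F2-isoprostane SD of 20 against the 50 pg/ml in the main-trial calculation. If these are different quantities, say so. If either SD is revised, recompute the slope, the correlation and the power together, because the figures in the wording above would no longer hold.

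The cost is one restated sentence and a check of two SDs. It needs no additional patients and no change of design, and the planned report on the first 80 subjects can stay.

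### The endothelial sub-study's FMD power inputs fit together only at a baseline-postoperative correlation of about 0.95 or more, and Aim 3 states neither its SD nor its FMD measure

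*Combined protocol and SAP*

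**What the plan says.** All three power statements stand in one paragraph of Section 10.0, under Sample Size Calculations.

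- **Aim 1** (80 patients) concerns a 2% "difference in FMD change from baseline to ICU admission between subjects randomized" to the two oxygenation groups, "with a standard deviation of 3.0%, with a type I error rate of 0.05". The claimed power is above 80%. The prior antioxidant study cited there had an SD of 2.0% for FMD improvement.
- **Aim 2** (80 patients) claims 94% power for a correlation of 0.2 between intraoperative F₂-isoprostanes and postoperative FMD, "with standard deviation of 20 pg/ml F₂I and 10 for regression errors". The 10 carries no unit.
- **Aim 3** reads: "We will have greater than 80% power to detect a 2% difference in FMD between patients who do and do not develop postoperative delirium", "assuming a delirium incidence of 23.4% among all ROCS trial subjects". No SD is given, and FMD is not specified as a level or a change.

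On sample size: "Sub-study Aims 1 and 2 will be completed with 80 ROCS trial subjects and sub-study Aim 3 with all 200 patients".

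Two statements in the Data Analysis Plan bear on this. The Aim 2 regression will adjust for baseline endothelial function and for confounders that include randomized group. For Aim 3, "we will compare baseline, postoperative, and change from baseline FMD" and other vascular measures with the organ-injury outcomes.

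**The concern.** The three aims draw on the same FMD measurements, so the spreads assumed for them should be mutually consistent. Aim 1 assumes 3.0% for change. Aim 2, as its 94% appears to have been computed, assumes an error SD of 10 for postoperative FMD, which is the only spread that the plan ties to the postoperative level. Aim 3 gives none, and its claim holds or fails according to which of the two is borrowed.

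If the larger value is right, a null delirium comparison on postoperative FMD could be read as backed by more than 80% power when the true figure is near 20%. If the smaller value also describes postoperative FMD, the Aim 2 calculation assumes an effect that cannot occur.

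**Working it through.** **Inputs from Section 10.0:** a 2% difference; SD 3.0% for change; 80 patients, taken as 40 per arm; F₂-isoprostane SD 20 pg/ml; error SD 10; delirium 23.4% of 200, so 47 against 153; two-sided α = 0.05. Power uses the noncentral t distribution.

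**1. Aim 1 reproduces.** With 40 per arm, difference 2 and SD 3.0, power is 83.8%, which agrees with the claim of more than 80%.

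**2. Aim 2 reproduces as a slope.**
- Noncentrality = slope × SD(x) × √n / SD(error) = 0.2 × 20 × √80 / 10 = 3.58. Power is 94.2%, matching the printed 94%.
- A true correlation of 0.2 with n = 80 gives only about 43%.

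So 0.2 was used as a slope per pg/ml and 10 as the SD of the regression errors, which are in the units of the outcome.

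**3. Implied spread of postoperative FMD.** The predictor contributes an SD of 0.2 × 20 = 4. The total is √(4² + 10²) = √116 = 10.8. The implied correlation is 4/10.8 = 0.37. Conversely, if postoperative FMD had an SD near 3%, this slope could not hold, because it alone contributes 4.

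**4. Can 3.0 and 10-10.8 coexist?** Let a and b be the baseline and postoperative SDs and ρ their correlation.
- Var(change) = a² + b² − 2ρab. For given b and ρ this is smallest at a = ρb, where it equals b²(1 − ρ²).
- An SD of change of 3.0 therefore needs ρ ≥ √(1 − 9/b²), whatever the baseline SD.
- b = 10 gives ρ ≥ 0.954; b = 10.8 gives ρ ≥ 0.960.

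The plan states no such correlation.

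**5. If the 10 comes from the planned Aim 2 model.** Once baseline FMD is a covariate, the postoperative value and the change have the same residuals, because they differ only by a quantity already in the model. The error SD then cannot exceed the SD of change. Since that model also includes randomized group, the within-group SD from Aim 1 is the right comparator, and 10 ≤ 3.0 is false. With an SD of change of 10, Aim 1 power at 40 per arm is 14%.

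**6. Aim 3** (47 against 153, difference 2):

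| FMD SD | Power |
|---|---|
| 3.0 | 97.8% |
| 4.0 | 84.7% |
| 4.26 | 80% |
| 10 | 22% |
| 10.8 | 20% |

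The difference detectable with 80% power is about 2.82 × SD × √(1/47 + 1/153) = 2.82 × SD × 0.167, which is about 4.7% at SD 10 and 5.1% at SD 10.8.

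**The case against.** The strongest reply is that no printed figure has been shown to be wrong.

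- An SD of change and an error SD for a level are different quantities, so a reader who infers that 3.0 and 10 can never both hold goes too far. This stands for an unadjusted regression. The sample size paragraph does not say which model produced the 10, so the outright contradiction in step 5 is conditional.
- A reader might also infer that Aim 3 really has 20% power. The documents do not support that. The sentence says only FMD, it shares the 2% effect and the paragraph with Aim 1, and change in FMD is among the planned comparisons. With SD 3.0 the claim is correct at 98%.
- The 10 has no unit. Power depends only on slope × 20 / error SD, so rescaling the slope and the error together leaves 94% unchanged. Reading the 10 in FMD percentage points is therefore an inference.
- The cited 2.0% and the chosen 3.0% favour the smaller spread, so the fault may lie in the Aim 2 inputs alone. That is quite possible.
- Aim 1 states the SD of its own endpoint. Inferring that Aim 1 is underpowered would mean overriding that value with one derived from Aim 2, using correlations that the documents do not give.
- The stakes are limited. Aim 3 is an association analysis in a cohort sized by the main trial, and the plan commits to point estimates with 95% confidence intervals.

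These replies limit the claim but do not remove it. The plan's only spread for postoperative FMD is more than twice what Aim 3 tolerates (10 against 4.26), and postoperative FMD is one of the measures that Aim 3 will compare.

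**Conclusion.** The sub-study's FMD inputs are not reconciled. Taking the 10 in FMD percentage points, they need a baseline-postoperative correlation of about 0.95-0.96 or more, which the plan neither states nor supports. Under the plan's own baseline-adjusted model they contradict each other, so at least one input behind a printed power figure would be wrong.

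The Aim 3 claim cannot be verified as written. Its power is 98% for an FMD measure with SD 3.0, such as change, and about 20-22% for postoperative FMD with SD 10-10.8. The documents do not show which value is right, so the finding is an inconsistency and an unstated input, not a demonstrated shortfall in power. It is worth correcting before the sub-study results are interpreted. It does not touch the main trial's sample size.

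**What to change.** Use one sourced set of FMD inputs for all three aims: the SD of postoperative FMD, the SD of change, and the baseline-postoperative correlation. Give the unit of the Aim 2 error SD, say whether its model is baseline-adjusted, and call the 0.2 a slope if that is what it is. State which FMD measure and SD the Aim 3 power refers to. Then restate the figures.

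- **If the FMD SD is about 3%:** write it into the Aim 3 sentence, with power of about 98%, and replace the Aim 2 inputs with compatible ones. For example, error SD 3 and slope 0.06 give 0.06 × 20 × √80 / 3 = 3.58, which keeps the 94%. No power figure need become less favourable.
- **If the SD of postoperative FMD is about 10:** restate Aim 3 on postoperative FMD as about 20% power for a 2% difference, or 80% power for about 5%, and justify the 3.0% used in Aim 1. If the SD of change is in fact 10 or more, Aim 1 power is at most about 14% and should be reported as such.

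The cost is one reworded paragraph and a short recalculation, with no extra patients or procedures and no change in sample size.

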We will recruit and randomize 200 cardiac surgery subjects to hyper-oxygenation ($\text{FIO}_2 = 0.8-1.0$, usual care) or physiologic oxygenation (minimum FIO_2 required to saturate arterial hemoglobin 95-97% and maintain a PaO_2 between 80-110 mmHg) during surgery. We will compare postoperative changes in serum creatinine and markers of nephron injury (neutrophil gelatinase-associated lipocalin [NGAL], between subjects randomized to physiologic oxygenation or hyper-oxygenation to test the hypothesis that maintaining physiologic oxygenation during anesthesia for cardiac surgery decreases postoperative kidney injury. To assess tissue oxygenation in the two study groups, we will continuously measure (automatically recorded every 5 seconds) the FIO_2 , SpO_2 , brain O_2 saturation, and muscle O_2 saturation. In addition, we will measure the PaO_2 , cardiac output, and arterial lactate prior to, during, and following surgery but no less frequently than every hour. We will compare these oxygenation metrics between subjects randomized to hyper-oxygenation vs. physiologic oxygenation to assess oxygen delivery and

consumption between groups. The primary endpoints of Aim 1 will be serum creatinine change (median +/- 95% confidence interval (CI)). Secondary endpoints include additional measures of AKI (incidence of AKI [defined using KDIGO criteria], neutrophil gelatinase-associated lipocalin [NGAL], and insulin-like growth factor-binding protein 7 [IGFBP7]/tissue inhibitor of metalloproteinases-2 [TIMP-2]), incidence of delirium (measured using CAM-ICU), duration of mechanical ventilation, duration of hospitalization, SpO₂ (median +/- 95% CI and area-under-the-curve (AUC) < 90%), PaO₂ (median +/- 95% CI, AUC > 150 mmHg, and AUC < 70 mmHg), brain and muscle O₂ saturation (median +/- 95% CI and AUC < 80% baseline), and the percent of FIO₂ titrations within protocol (protocol adherence). Safety endpoints will focus on any risk of hypoxia between study groups and will include postoperative serum CK-MB measurements and rates of arrhythmias, reintubation, transient ischemic attack, stroke, and death.

Aim 2: Test the hypothesis that physiologic oxygenation during cardiac surgery reduces the generation of superoxide (measured by electron paramagnetic resonance of CAT-1H and TMH electron spin probes) and systemic oxidative stress (measured by plasma concentrations of F₂-isoprostanes and isofurans).

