Change in serum creatinine from baseline to postoperative day 2 (Aim 1 primary endpoint) will be compared between normoxia and hyperoxia study groups using the Wilcoxon rank sum test. Plasma concentrations of F₂-isoprostanes and isofurans (Aim 2 primary endpoint) will be compared between normoxia and hyperoxia study groups using a mixed effects regression analysis, adjusting for collection time as a categorical variable (i.e., study phase). This method allows for simultaneous evaluation of multiple correlated measurements per subject, and between-subject heterogeneity in the effects of treatment on markers of oxidative stress. Specifically, we will use a random intercept and random 'slope' for treatment allocation, indexed by study subject. Analysis of the effects of treatment on change in creatinine and on oxidative stress will be repeated separately within randomization strata.

We will evaluate treatment effect on additional markers of AKI (AKI incidence using KDIGO criteria, urine concentrations of NGAL and IGFBP-7/TEMP2, use of dialysis), delirium incidence and duration (diagnosed with CAM-ICU), and myocardial damage (quantified by measuring CK-MB on the morning of the day after surgery) as secondary analyses.

To assess effect of treatment on oxygenation and perfusion we will compare SpO₂, PO₂, cerebral oxygenation, muscle oxygenation, mixed venous hemoglobin saturation, cardiac output, and arterial lactate concentrations between normoxia and hyperoxia groups using mixed effects regression analysis as described above for plasma concentrations of F₂-isoprostanes and isofurans.

We will also compare differences in ROS production, mitochondrial function, atrial fibrillation, stroke, pneumonia, wound infection, time-to-extubation, duration of ICU stay, and in-hospital mortality as well as pain scales, depression data, and neurocognitive function between normoxia and hyperoxia groups as secondary endpoints. We will compare safety endpoints myocardial infarction, transient

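### Clopper-Pearson is named for between-group effects but covers only a single proportion, and no interval is named to match the Wilcoxon test on the Aim 1 primary endpoint

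*Combined protocol and SAP*

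**What the plan says.** In section 10.0 (Data Analysis Plan), single-time-point outcomes are to be compared by "Fisher's exact test or Pearson chi-square test for categorical variables, and the Wilcoxon rank sum test or Student T-test for quantitative outcomes, as appropriate". The next sentence covers intervals: "The Clopper-Pearson and Wald methods will be used to construct 95% confidence intervals for the between group effects". It does not say which method goes with which outcome.

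The Aim 1 primary endpoint, creatinine change from baseline to postoperative day 2, "will be compared between normoxia and hyperoxia study groups using the Wilcoxon rank sum test". Section 2.0 describes the same endpoint as a median with a 95% interval. Neither section names a between-group effect measure for it: a Hodges-Lehmann shift, a difference in medians or a difference in means.

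The Aim 2 primary endpoint is analysed "using a mixed effects regression analysis, adjusting for collection time as a categorical variable". Later in section 10.0, logistic, proportional odds and linear regression are named for other outcomes.

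The section closes by resting inference on intervals: "Specific inferences on the effects of interest will be made by reporting point estimates, along with 95% confidence intervals".

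**The concern.** There are three separate gaps.

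- **Clopper-Pearson.** It inverts the binomial test for one proportion. Applied to two arms, it returns two intervals and none for the contrast. Nothing in the plan limits it to within-arm proportions; it is tied expressly to between-group effects.
- **Wald on sparse binary outcomes.** If Clopper-Pearson drops out, Wald is the only named method left for a risk difference. The safety endpoints in section 6.0 (stroke, transient ischemic attack, Q-wave infarction, reintubation, death) may be rare, and there the Wald interval behaves badly.
- **Aim 1 primary endpoint.** The test is rank-based, but no rank-based estimate or interval is named. The estimate reported beside the primary p-value is therefore left open until the data are in hand.

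The stake is the reported effect sizes. The plan says that its inferences will be made through estimates and intervals, so these should be fixed in advance and should belong with the tests beside them.

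**Working it through.** **Inputs.** From section 10.0: N = 200, difference 0.15 mg/dl, SD 0.375, 80% power, two-sided alpha 0.05. Assumed: 1:1 allocation, so 100 per arm (two arms with blocks of two or four; the ratio is not stated). The event counts below are illustrations. The lognormal skew is an assumption, because the documents give only a mean and SD for creatinine change.

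**1. The plan's own figure.** n per arm = 2(1.960 + 0.842)² × (0.375/0.15)² = 2 × 7.85 × 6.25 = 98.1, so 99. Power with 100 per arm = Φ(0.15/(0.375√(2/100)) − 1.96) = Φ(2.828 − 1.960) = 80.7% (80.4% by t-test). The stated 80% reproduces and is not in dispute.

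**2. What Clopper-Pearson returns.** For 30/100 against 18/100 it gives 21.2% to 40.0% in one arm and 11.0% to 26.9% in the other. It gives no interval for the 12-point difference.

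**3. Wald risk difference at moderate rates.** d ± 1.96√(p₁q₁/n + p₂q₂/n). For 34/100 against 20/100: 0.14 ± 1.96 × √(0.002244 + 0.0016) = 0.14 ± 1.96 × 0.062, or 1.8 to 26.2 points. Newcombe gives 1.7 to 25.8 and Fisher p = 0.038. Wald is adequate here.

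**4. Wald risk difference with sparse events.** For 4/100 against 0/100: 0.04 ± 1.96 × √(0.04 × 0.96/100) = 0.04 ± 1.96 × 0.0196, or 0.2 to 7.8 points, which excludes zero. The Newcombe interval is built from the Wilson limits of each arm (1.57% to 9.84%, and 0 to 3.70%):

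- lower limit: 4.0 − √((4.0 − 1.57)² + 3.70²) = −0.4 points
- upper limit: 4.0 + (9.84 − 4.0) = 9.8 points

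Fisher p = 0.12. By exact enumeration at a true 2% in both arms, Wald excludes zero in 4.0% of trials and Fisher rejects in 0.5%. If neither arm has an event, the Wald interval has zero width. At a true 1% rate this happens with probability 0.99²⁰⁰ = 13%.

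**5. Wald mean difference against the Wilcoxon decision on creatinine.** Simulation, 100 per arm, SD 0.375, 10,000 trials per scenario:

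| Data | True shift (mg/dl) | Wilcoxon significant | Wald excludes 0 | Disagree |
|---|---|---|---|---|
| Normal | 0 | 5.0% | 5.2% | 1.9% |
| Normal | 0.15 | 79.1% | 81.8% | 5.0% |
| Lognormal, log-SD 0.5 | 0 | 4.9% | 4.9% | 3.6% |
| Lognormal, log-SD 0.5 | 0.15 | 93.9% | 81.0% | 13.5% |
| Lognormal, log-SD 0.8 | 0 | 5.1% | 5.2% | 5.1% |
| Lognormal, log-SD 0.8 | 0.15 | 99.8% | 81.7% | 18.1% |
| Lognormal, log-SD 1.0 | 0 | 5.1% | 4.8% | 5.7% |
| Lognormal, log-SD 1.0 | 0.15 | 100% | 82.4% | 17.6% |

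Under skew at the 0.15 shift, nearly all disagreement is a significant Wilcoxon test beside a Wald interval that includes zero.

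**6. The matched interval.** The Hodges-Lehmann estimate is the median of the 100 × 100 pairwise differences. Its limits are the k-th smallest and k-th largest, with k = ⌊n²/2 − 1.96√(n²(2n+1)/12)⌋ = ⌊5000 − 1.96 × 409.3⌋ = 4197. In 5,000 trials at the 0.15 shift, disagreement with Wilcoxon was 0.2% (normal) and 0% (log-SD 0.8). Coverage was 95.5% and 94.6%.

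**The case against.** The strongest reply is that the sentence names two methods, and Wald does give a valid large-sample interval for a between-group effect. Step 3 shows it within half a point of Newcombe at moderate event rates. In step 5 it kept 4.8% to 5.2% rejections under no effect, skewed or not. It is also the standard choice for the Aim 2 mixed model and the secondary regressions. All of this stands.

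A reader might infer that the reported intervals would be invalid, or would contradict the p-values. The documents do not support that. The sentence is generic, closes a paragraph on single-time-point outcomes, and does not assign Wald to the Wilcoxon endpoint. Where the two differ, they answer different questions: a mean difference against a rank-based shift. For creatinine, the fair description is an unspecified interval that can differ from the test.

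A reader might also infer that effects will be judged by whether the two Clopper-Pearson arm intervals overlap. The plan proposes no such rule; it prescribes Fisher, chi-square and logistic regression. Larger disagreement on creatinine can be produced by assuming a shift below the planned 0.15 mg/dl, but that adds a second assumption to the assumed skew.

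Nor does a better interval guarantee agreement with Fisher. For 30/100 against 18/100, Newcombe (0.1 to 23.5 points) and Wald (0.3 to 23.7) both exclude zero while Fisher p = 0.068. The case for Newcombe or Miettinen-Nurminen rests on sparse events, not on matching every p-value.

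The reply does not cover the misuse of Clopper-Pearson, the sparse safety events, or the missing estimator for the primary endpoint.

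**Conclusion.** The point holds as a defect of specification and reporting. The Clopper-Pearson part of the rule is wrong as written, since it yields no interval for any two-arm contrast. The Wald part is sound for mean differences, model coefficients and risk differences at moderate rates, and unreliable for sparse safety events. The Aim 1 primary endpoint has no stated effect measure and no interval matched to its test.

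If a Wald mean-difference interval were used for Aim 1, it would disagree with Wilcoxon on significance in about 5% of trials with normal data and about 13-18% with lognormal skew (log-SD 0.5 to 1.0), at the planned 0.15 mg/dl shift. The second range rests on assumed skew, and both figures assume 100 per arm. The primary test, alpha, power and sample size are untouched.

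**What to change.** Replace the single sentence on intervals in section 10.0 with a rule by type of outcome:

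- **Within-arm proportions:** Clopper-Pearson, for this purpose only.
- **Binary between-group effects, including safety events:** risk difference with a Newcombe or Miettinen-Nurminen 95% interval.
- **Aim 1 creatinine change:** Hodges-Lehmann shift with the 95% interval from inverting the Wilcoxon test. State that this is the between-group estimate and that the medians in section 2.0 are descriptive, since the shift is not in general the difference of the two medians.
- **Mixed-model and regression coefficients:** Wald intervals from the fitted model.

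The cost is a few lines of wording, settled before unblinding. All these methods are available in R, which the plan already names. No sample size, test or significance level changes.
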